5.2 Important notes regarding enrollment

- 1) Enrollments after the initiation of the treatment protocol will not be permitted without exception.
- 2) When the enrollment and eligibility checklist content is unsatisfactory, the enrollment will not be accepted until it is all the content is satisfied.
- 3) After confirmation of eligibility, a registration number will be issued. Enrollment will be completed once the registration number has been issued.
- 4) Except in the event of withdrawal of consent, including the refusal of the use of data in the trial, patients will not be removed from the trial (erased from the database) once they have been enrolled. In the event of a double registration, the information from the first enrollment (registration number) will be used.

- 5) When a misregistration or double registration is discovered, the data management office should be contacted as soon as possible.
- 6) At the time of enrollment, in the event of an ongoing medical examination at another hospital or department, the attending physician is to be contacted and notified that the patient concerned is participating in the present trial.

6 Dosing schedule and combination therapy

If the safety of the subject is not at risk, treatment and changes to treatment will be carried out in accordance with the content of this chapter. If a medical emergency is identified when the present protocol is followed, the treatment will be changed in accordance the medical judgment of the principal investigator (or subinvestigator) for the trial (hereinafter "principal investigator").

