6.1.2 Recommended dose (RD) and transition to the expansion cohort

In the present trial, the starting dose of regorafenib will commence from level 1 (80 mg/day), and tolerability of combination therapy with nivolumab (3.0 mg/kg at 2-week intervals) will be verified. One cycle will last 28 days and DLT will be evaluated using a 3 + 3 design for the following doses to verify tolerability.

Level 1

Regorafenib: Oral administration at a dose of 80 mg given once per day for 21 consecutive days,

with a 1-week washout period.

Nivolumab: Given once every 2 weeks at a dose of 3.0 mg/kg via an intravenous infusion.

When it is deemed that there is no problem with safety at the doses described above, tolerability will be verified at the level-2 dosages described below.

Level 2

Regorafenib: Oral administration at a dose of 120 mg/day for 21 consecutive days, with a 1-week washout period.

Nivolumab: Given once every 2 weeks at a dose of 3.0 mg/kg.

When it is deemed that there is no problem with safety at the doses described above, tolerability will be verified at the level-3 dosages described below.

Level 3

Regorafenib: Oral administration at a dose of 160 mg/day for 21 consecutive days, with a 1-week washout period.

Nivolumab: Given once every 2 weeks at a dose of 3.0 mg/kg.

After starting the trial, three cases are registered at level 1, and temporary case registration is suspended until safety evaluation of the first course is completed in all cases. If there are cases in which evaluation of DLT cannot be performed properly, such as being canceled due to reasons other than safety during the course of the first course, the necessary number of cases is appropriately added to the administration level.

1) In cases where no DLT is observed in 3 cases, registration of the case is started at the next dose level, and the same procedure is repeated until MTD is reached with level 3 as the upper limit.

2) When DLT is observed in 2 cases or more in 3 cases, the administration level is judged as MTD.

3) If DLT is observed in 1 out of 3 cases, 3 further cases are additionally registered at the administration level (total 6 cases). When DLT is observed in 2 out of 6 cases, the administration level is judged as MTD. However, if there are two cases of DLT-expressing cases before the number of registered cases at the administration level reaches 6, the administration level is judged as MTD at that time point.

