6.1.4 Target subjects for DLT evaluation

For each level, at least three subjects will be enrolled, and the presence or absence of DLT will be evaluated during the DLT evaluation period.

When it is determined that there is a subject who will not change levels, an additional subject will

be enrolled to evaluate the DLT determined in 6.1.3.

Furthermore, among the enrolled subjects, those who meet the following conditions will be excluded from DLT evaluation:

1) Subjects who are unable to receive regorafenib for ≥ 14 days in the first course for reasons other than toxicity.

2) Subjects for whom sufficient data cannot be obtained to determine the DLT evaluation because of missing mandatory tests, etc.

3) Cases in which adequate data for DLT evaluation judgment could not be obtained due to essential test defects

Furthermore, among the participants who withdraw from regorafenib and nivolumab during the first course for reasons other than adverse events or who withdraw from treatment for a long period because of toxicities other than DLT, the decision to subject such patients to a DLT evaluation will be determined upon deliberation between the trial coordinating committee and the participating institution.

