12.2 All enrolled patients

"All enrolled patients" are defined as patients enrolled in this study in accordance with Section "5.

Enrollment," excluding those who have been enrolled multiple times or mistakenly enrolled.

| 10 0 | D | • . • | e | | | |
|------|-------|-------|-------|---------|-------|---------|
| 12.5 | Defin | ition | of an | 9 VCIC | nonii | lations |
| 14.0 | Dum | nuon | or an | ary 515 | popu | autons |

Each analysis population is defined below.

| Abbreviation | Analysis population | Definition |
|--------------|---------------------|---|
| None | DLT analysis set | See Section "6. Treatment Regimen and |
| | | Treatment Modification Criteria." |
| SP | Safety population | The population of patients who received |
| | | the investigational product at least once |
| | | among all enrolled patients. |
| FAS | Full analysis set | The population of patients that excludes |
| | | those to whom the following applies |
| | | from all enrolled patients: |
| | | • Patients who should have been judged |
| | | as clearly ineligible based on the |
| | | information before enrollment |
| | | (ineligible patients). |

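### As worded, the safety population leaves out dosed patients enrolled in error or twice, and Section 5.2 does not settle when a dosed patient's data may be erased

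*Combined protocol and SAP*

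**What the plan says.** Four parts of the combined protocol and SAP bear on this.

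- **Section 5.2, item 4** governs removal: "Except in the event of withdrawal of consent, including the refusal of the use of data in the trial, patients will not be removed". Removal here means being "erased from the database) once they have been enrolled". The next sentence deals with duplicates: "In the event of a double registration, the information from the first enrollment (registration number) will be used".
- **Section 12.2** defines the all-enrolled set as patients enrolled under Section 5, "excluding those who have been enrolled multiple times or mistakenly enrolled".
- **Section 12.3** defines the SP as patients who had the investigational product at least once, "among all enrolled patients". The full analysis set (FAS) separately excludes patients who were clearly ineligible on pre-enrollment information. The DLT analysis set is defined by reference to Section 6, not to Section 12.2.
- **Sections 12.6.1 and 12.12.2** use the SP for safety. AE occurrence is summarised in the SP, and the study report gives both DLT and AE incidences, by worst grade, under the SP heading.

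Section 6 has its own rules on who counts for DLT. Section 6.1.4 excludes "Subjects for whom sufficient data cannot be obtained to determine the DLT evaluation because of missing mandatory tests, etc". Under Section 6.1.2, when DLT cannot be properly evaluated, "the necessary number of cases is appropriately added to the administration level".

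**The concern.** A safety set should contain everyone exposed to the drug, because an administrative error at registration does not undo the exposure. Here the SP inherits an exclusion written for enrollment bookkeeping, and the primary objective of this phase I trial is safety and tolerability. Separately, a patient may withdraw consent because of toxicity. If that permits erasure, the patients most likely to be lost are those with events, and the reported incidences would be too low.

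The loss might also go unseen. The report appendix in Section 12.12.2 lists discontinued patients and patients excluded from the FAS, but neither patients left out of the SP nor patients erased from the database.

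**Working it through.** No power, alpha or sample size in the plan depends on these definitions, so there is no planned figure to reproduce. The check is mainly a comparison of the text.

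**1. Patient enrolled in error who was dosed.** Section 12.2 takes the patient out of the all-enrolled set. Section 12.3 draws the SP from that set, so the patient is outside the SP. Section 12.12.2 reports AE and DLT incidences in the SP, so the patient is in neither table. The plan does not define enrollment in error. It seems to differ from ineligibility, which is a separate exclusion applying only to the FAS.

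**2. Patient registered twice who was dosed.** Section 12.2, read literally, excludes the person. Section 5.2 item 4 keeps the information from the first registration. Both cannot be followed as written. Section 12.2 may mean only the duplicate record, but it does not say so.

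**3. Withdrawal of consent.** The exception in Section 5.2 item 4 has two readings.

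- Wide: refusal of data use is one case among others, so any withdrawal of consent permits erasure.
- Narrow: only a withdrawal that extends to data use permits it.

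Item 4 does not exempt dosed patients or say that data up to withdrawal are kept. Section 2.8 adds a case: dose-escalation patients must consent again to continue after the DLT period, and the protocol does not say whether declining is a withdrawal of consent under Section 5.2.

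**4. Size in the reported tables.** Inputs: up to 6 patients per level and about 30 in expansion (Section 12.8). The event counts are assumed.

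| All dosed patients kept | One patient with an event omitted | One patient without an event omitted |
|---|---|---|
| 2/6 = 33.3% | 1/5 = 20.0% | 2/5 = 40.0% |
| 1/6 = 16.7% | 0/5 = 0% | 1/5 = 20.0% |
| 3/30 = 10.0% | 2/29 = 6.9% | 3/29 = 10.3% |
| 1/30 = 3.3% | 0/29 = 0% | 1/29 = 3.4% |

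The direction depends on who is omitted. Nothing in the documents links misregistration to toxicity, whereas withdrawal of consent could be linked to it.

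**5. Illustration for escalation only.** Suppose a fraction q of patients with a DLT were erased and replaced before the level decision. With true DLT probability p, the apparent probability is p' = p(1−q)/(1−pq). A level passes the 3+3 rule with probability (1−p')³ + 3p'(1−p')²(1−p')³.

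- p = 0.33, q = 0: 0.301 + 0.444 × 0.301 = 0.434.
- p = 0.33, q = 0.10: p' = 0.297/0.967 = 0.307, passing probability 0.480.
- p = 0.33, q = 0.20: p' = 0.264/0.934 = 0.283, passing probability 0.530.

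The documents give neither p nor q, and the replacement step is not in the text for a patient with an observed DLT.

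**The case against.** The strongest reply is that the plan, read as a whole, keeps most of these patients.

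- **Stopping by choice.** Section 6.2.1 item 2 treats a request to stop as termination of treatment, Section 6.2.2 records its reason on the CRF, Section 11.2.3 has a censoring rule for patients who refuse to go on and start another treatment, and Section 12.12.2 lists discontinued patients. This favours the narrow reading of Section 5.2 and stands as far as it goes: ordinary withdrawal is not shown to cause erasure. The sentence still permits the wide reading.
- **Double registration.** Keeping the first registration is the workable rule. That stands, and what remains is a conflict to reconcile.
- **Enrollment in error is rare.** Under Section 5.2 a registration number follows confirmation of eligibility, misregistrations must be reported promptly, and ineligible patients stay in the SP. This limits how often the problem arises but does not change the definition.
- **Serious events have another channel.** Section 10.2.2 sends them to the coordinating committee within 24 hours. That stands, but non-serious events have no such route.

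A reader might infer that a patient with a DLT could be erased and replaced, turning a failed level into a passed one. The text does not support this. The DLT set comes from Section 6. The replacement example in Section 6.1.2 and the first exclusion in Section 6.1.4 concern reasons other than safety or toxicity. The missing-data exclusion concerns tests that were not done, not a DLT already established. Section 12.5 places level decisions within monitoring, so a later erasure could change the reported table but not a decision already taken. Nor does erasure alone turn 1/3 into 0/3: it gives 0/2, and 0/3 needs a replacement without a DLT.

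**Conclusion.** The point holds for reporting. Followed literally, Sections 12.2, 12.3 and 12.12.2 leave a dosed patient who was misregistered or registered twice out of the AE and DLT incidence tables, and for double registration Section 12.2 contradicts Section 5.2. Section 5.2 item 4 is also ambiguous about erasing a dosed patient's data on withdrawal of consent, which could alter the same tables.

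One omitted patient with an event moves a reported incidence by 13 to 17 percentage points at a level of six (33.3% to 20.0%, or 16.7% to 0%) and by about 3 points in a cohort of 30. These sizes rest on assumed event counts and a single omission; the documents give no frequency for misregistration or erasure. An effect on escalation decisions is not shown, and the 3+3 probabilities are illustration only. The consent form and Section 5.1 were not in the text available to me, so nothing here rests on their silence.

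**What to change.** 1. **Section 12.3:** define the SP as every person who received at least one dose of either study drug, regardless of any enrollment error.
2. **Section 12.2:** limit the exclusion for multiple enrollment to duplicate records, and keep the patient under the first registration number, in line with Section 5.2.
3. **Section 5.2, item 4:** state that data collected up to withdrawal of consent are kept and that erasure follows only an explicit refusal of data use. Report the number of patients erased by dose level and, as far as consent and regulations allow, whether a DLT had already been adjudicated. This also covers a patient who had a DLT and then refuses data use, whose individual data cannot simply be retained in the count.

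The cost is wording, and possibly one line in the consent text on keeping data up to withdrawal. Sample size and schedule do not change.

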6.1 Protocol treatment

In the present trial, the protocol treatment will consist of the investigational drug, nivolumab, used in combination with regorafenib. However, in the event that the termination criteria are satisfied for one of these drugs, the trial investigator can consider continuing the treatment protocol with either nivolumab or regorafenib monotherapy upon deliberation with the trial coordinating committee. The treatment protocol will commence within 14 days of enrollment, including the day of enrollment. Furthermore, in the event that administration of the investigational drug cannot be initiated within 14 days of enrollment (including the day of enrollment), the trial coordinating committee is to be contacted to examine how the patient should be handled.

The following terminology is used in the present protocol:

- Termination: Administration of the investigational drug is not resumed.
- Washout: Omission of one or more doses of the investigational drug and moving onto the next dosing schedule.

• Washout period: The duration of time that the investigational drug is not administered.

6.1.1 Dosing and administration method

In the dose-escalation cohort, the stipulated doses for each level are shown in Table 6.1.1a. At least 1 day will be left between the initial starting day of the trial protocol (cycle 1 day 1) for the first and second patient in each level. The expansion cohort will be given the clinically RD determined on the basis of the results of the dose-escalation cohort. The method of determining the clinical RD is described in section 7.1.2.

The dose administered to each individual subject will be calculated according to body weight at the time of enrollment. However, in the event of a change in body weight of >10% as measured on day 1 of each cycle compared with that at the time of enrollment, the dose will be calculated according to the new body weight. Thereafter, the same action will be taken, upon observation of a change of over 10% in body weight compared with the most recent body weight change. The administered dose (mg units) will be calculated and rounded to two decimal places.

| Level | Nivolumab dose | Regorafenib dose | Target number of subjects |
|-------|----------------|------------------|---------------------------|
| | | | for the DLT evaluation |
| 1 | 3.0 mg/kg | 80 mg/day | 3–6 |
| 2 | 3.0 mg/kg | 120 mg/day | 3–6 |
| 3 | 3.0 mg/kg | 160 mg/day | 3–6 |

Table 6.1.1a Doses of nivolumab and regorafenib

Regorafenib will be administered with water once per day after eating (low-fat meal recommended) at a dose of 80 mg (level 1), 120 mg (level 2), or 160 mg (level 3). Regorafenib will be given orally for 21 consecutive days, followed by a washout period of 7 days. In the event of withdrawal because of adverse events, the period of withdrawal will be included in the 21-day oral therapy period, and will be followed by a washout period of seven days.

Nivolumab will be administered via intravenous infusion given once every 2 weeks at a dose of 3.0 mg/kg over a 30 min period after 1 h (up to 2 h permissible) has passed because the oral administration of regorafenib in the morning. The dosing period will be set to as close to 30 min as possible (25–40 min) by the medical institution administering the treatment.

For precautions regarding dosing, refer to "Patient instructions regarding the handling of the investigational drug."

From cycle 2 onward, the treatment will commence after verifying that the dosing criteria listed in section 6.3 have been satisfied. The start day for nivolumab will be defined as day 1, including the washout period even in the event of conflict with the criteria defined in 6.3, and one cycle will last 28 days. If nivolumab is terminated and treatment is resumed as regorafenib monotherapy, the subsequent day of regorafenib resumption will be defined as day 1. In such an instance one cycle will also last 28 days.

Treatment will continue until the "criteria for treatment termination" are satisfied.

6.1.2 Recommended dose (RD) and transition to the expansion cohort

In the present trial, the starting dose of regorafenib will commence from level 1 (80 mg/day), and tolerability of combination therapy with nivolumab (3.0 mg/kg at 2-week intervals) will be verified. One cycle will last 28 days and DLT will be evaluated using a 3 + 3 design for the following doses to verify tolerability.

Level 1

Regorafenib: Oral administration at a dose of 80 mg given once per day for 21 consecutive days,

with a 1-week washout period.

Nivolumab: Given once every 2 weeks at a dose of 3.0 mg/kg via an intravenous infusion.

When it is deemed that there is no problem with safety at the doses described above, tolerability will be verified at the level-2 dosages described below.

Level 2

Regorafenib: Oral administration at a dose of 120 mg/day for 21 consecutive days, with a 1-week washout period.

Nivolumab: Given once every 2 weeks at a dose of 3.0 mg/kg.

When it is deemed that there is no problem with safety at the doses described above, tolerability will be verified at the level-3 dosages described below.

Level 3

Regorafenib: Oral administration at a dose of 160 mg/day for 21 consecutive days, with a 1-week washout period.

Nivolumab: Given once every 2 weeks at a dose of 3.0 mg/kg.

After starting the trial, three cases are registered at level 1, and temporary case registration is suspended until safety evaluation of the first course is completed in all cases. If there are cases in which evaluation of DLT cannot be performed properly, such as being canceled due to reasons other than safety during the course of the first course, the necessary number of cases is appropriately added to the administration level.

1) In cases where no DLT is observed in 3 cases, registration of the case is started at the next dose level, and the same procedure is repeated until MTD is reached with level 3 as the upper limit.

2) When DLT is observed in 2 cases or more in 3 cases, the administration level is judged as MTD.

3) If DLT is observed in 1 out of 3 cases, 3 further cases are additionally registered at the administration level (total 6 cases). When DLT is observed in 2 out of 6 cases, the administration level is judged as MTD. However, if there are two cases of DLT-expressing cases before the number of registered cases at the administration level reaches 6, the administration level is judged as MTD at that time point.

4) If it is judged that MTD is exceeded, 6 cases of DLT evaluation are already carried out at the level one level below and if the DLT is 1 case or less of 6 cases, the dose is taken as MTD and RD. At the relevant dose, if only 3 people are evaluating DLT, add 3 cases (total 6 cases). When the number of

DLT is 1 or less out of 6, the dose is defined as MTD and RD. If it is judged that Level 1 exceeds the MTD, review the dose or consider stopping the trial.

5) MTD should be the highest dose level of DLT expression less than 1 in 6 cases.

Expansion cohort: Implemented using the RD estimated in the dose-escalation cohort.

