| | observed via imaging or a new anticancer treatment is initiated, whichever happens |
| | first. |
| Sample size | Dose-escalation cohort: A total of 3–6 patients per level, for a total of 9–18 patients |
| | Expansion cohort: Approximately 30 patients in total |
| Administration | Dose-escalation cohort |
| method | One course will last 28 days*, and tolerability will be verified for the following |
| | dosages. |
| | Level 1 |
| | Regorafenib: Oral administration at a dose of 80 mg/day for 21 consecutive days, with |

| | a 1-week washout period. |
|-------------|--|
| | Nivolumab: Given once every 2 weeks at a dose of 3.0 mg/kg. |
| | When it is deemed that there are no safety issues associated with the above dosages, |
| | tolerability will be verified for the following level-2 dosages. |
| | Level 2 |
| | Regorafenib: Oral administration at a dose of 120 mg /day for 21 consecutive days, |
| | with a 1-week washout period. |
| | Nivolumab: Given once every 2 weeks at a dose of 3.0 mg/kg. |
| | Level 3 |
| | Regorafenib: Oral administration at a dose of 160 mg /day for 21 consecutive days, |
| | with a 1-week washout period. |
| | Nivolumab: Given once every 2 weeks at a dose of 3.0 mg/kg. |
| | When tolerability has been confirmed for the level-3 dosages, the above dosages will |
| | be the recommended dosages. |
| | |
| | The administered dose will increase using a $3 + 3$ design in accordance with the DLT. |
| | Three or more patients will be enrolled at each level. In the event that DLT is not |
| | observed during the initial course in the first three patients, these patients will move |
| | onto the next level. In the event that DLT is observed in one of the first three patients, |
| | an additional three patients will be added to the level in question. When all three |
| | additional patients have completed the first course without presenting with any DLT, |
| | these patients will move onto the next level. If DLT is observed in one of the three |
| | additional patients, an additional three patients will be added to the level below to |
| | determine the MTD. |
| | |
| | Expansion cohort: The trial will be conducted using the estimated RD found in the |
| | dose-escalation cohort. |
| Safety | Evaluations will be performed using CTCAE version 4.03. |
| evaluation: | |
| Efficacy | The antitumor effect will be evaluated in accordance with irRECIST and RECIST |

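### Section 6.1.2 gives conflicting definitions of the MTD and does not say whether 0/3 DLTs at level 3 is enough, so the primary endpoint has no single decision rule

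*Combined protocol and SAP*

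**What the plan says.** The primary endpoint in section 1 (Objectives) is the MTD and RD of regorafenib, based on DLTs. Section 6.1.2 sets the rule for a 3 + 3 design with three levels:

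- **Item 1.** 0/3 opens the next level, with level 3 as the ceiling. No outcome is given for 0/3 at level 3.
- **Items 2–3.** A level with two or more DLTs in three patients is itself called the MTD. For six patients, "When DLT is observed in 2 out of 6 cases, the administration level is judged as MTD". The same label applies as soon as two DLTs occur before six patients are registered.
- **Item 4.** It opens with "If it is judged that MTD is exceeded" and turns to the level below, brought up to six patients if needed. When the number of "DLT is 1 or less out of 6, the dose is defined as MTD and RD".
- **Item 5.** "MTD should be the highest dose level of DLT expression less than 1 in 6 cases".

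The Summary (Administration method) moves to the next level when all three "additional patients have completed the first course without presenting with any DLT". If a DLT occurs in one of the three "additional patients, an additional three patients will be added to the level below to" determine the MTD. On the top level it says "When tolerability has been confirmed for the level-3 dosages, the above dosages will" be the recommended ones, without a number of patients.

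Table 6.1.1a allows 3–6 patients at every level. The escalation total is 9–18 in the Summary and section 2.8.2, but 12–18 in section 12.8. Section 12.9 gives no rationale of its own and refers back to Section 6.

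**The concern.** There are three separate gaps.

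1. **Label.** Items 2–3 call the toxic level the MTD. Item 4 starts from a state, MTD exceeded, that items 1–3 never declare, and gives the MTD label to the level below.
2. **Threshold.** Item 4 accepts 1/6 and item 5, as written, does not. The Summary clears a level with 1/3 then 0/3 for escalation, yet under item 5 that level could never be the MTD. Section 6.1.2 itself does not say what follows 1/6.
3. **Top level.** Item 4 applies only after a level has failed, item 5 is stated per six patients, and the Summary gives no count. So 0/3 at level 3 is not settled.

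The RD is the dose for about 30 expansion patients. Within section 6.1.2 only item 4 names an RD, and it gives the MTD and RD together. A conflict over the MTD at exactly 1/6 therefore carries over to the RD.

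**Working it through.** **Planned totals.** Three levels × 3 = 9 and three levels × 6 = 18, which reproduces 9–18. The lower limit of 12 does not follow from three per level. It equals 3 + 3 + 6, that is, six patients required at one level.

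**One data set, several answers.** Take level 1 = 0/3, level 2 = 1/6 and level 3 = 2/6, all reachable under the stated steps.

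| Rule | MTD |
|---|---|
| Items 2–3 | level 3 |
| Item 4 | level 2 |
| Item 5, literal | level 1, or no level if six evaluated patients are required |

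The documents give no DLT rates, so every rate p below is an assumption; q = 1 − p.

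**Item 4 against item 5, one level with six patients.** Item 4 accepts with probability q⁶ + 6pq⁵, item 5 with q⁶. The gap is 6pq⁵, the chance of exactly 1/6.

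| p | Item 4 | Item 5 | Gap |
|---|---|---|---|
| 10% | 0.886 | 0.531 | 0.354 |
| 20% | 0.655 | 0.262 | 0.393 |
| 30% | 0.420 | 0.118 | 0.303 |

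**Level 3, once reached.** Acceptance is q³ + 3pq⁵ if 0/3 suffices and q⁶ + 6pq⁵ if six are required: 0.494 and 0.420 at p = 30%, 0.309 and 0.233 at p = 40%.

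**Whole escalation at 10/20/40%.** The rules are: escalate on 0/3 or 1/6, stop at two or more DLTs, expand the level below to six, accept at 1/6 or fewer, and repeat item 4 if the expanded level fails. The target is the chance that the declared level is 1 or 2 and has exactly 1/6. Figures are given first for 0/3 sufficing at level 3, then for six required.

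- Level 1 is passed: 0.729 + 3(0.1)(0.9⁵) = 0.906. Level 2 is passed: 0.512 + 3(0.2)(0.8⁵) = 0.709, so it fails with 0.291.
- Level 3 fails: 1 − 0.309 = 0.691; 1 − 0.233 = 0.767.
- Level 2 declared at 1/6: 0.906 × 0.393 × 0.691 = 0.246; with 0.767, 0.273.
- Level 1 declared at 1/6: 0.354 × [0.291 + 0.512 × 0.691 × 0.104] = 0.116; with 0.767, 0.118. Here 0.104 is the chance of two or more DLTs in the three patients added at level 2.
- Sums: 0.246 + 0.116 = 0.362 and 0.273 + 0.118 = 0.391.

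If item 4 is not repeated, the level 1 term is 0.354 × 0.291 = 0.103, and the sums are 0.349 and 0.376 (35% and 38%). Full enumeration gives the same results. Over rate sets from 5/10/20% to 15/30/45%, with repetition, the range is 12–41% if 0/3 suffices and 14–43% if six are required.

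**The case against.** The strongest reply is that the working rule can be inferred. Item 4 ends with what to do if level 1 exceeds the MTD. That sentence would be idle if a toxic level were itself the MTD, and the Summary also turns to the level below. On this view items 2–3 are a mislabel and item 5 is a translation slip, since item 4 states 1 or fewer of 6 twice. For level 3, the Summary treats 0/3 as passing a level, section 6.1.4 asks for at least three subjects per level, and 9–18 appears twice. The 12 in section 12.8 could be a plain error, or mean six at some other level.

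Much of this stands for the label. It does not correct item 5, which is worded as the definition of the MTD and collides with item 4 at 1/6, an ordinary 3 + 3 outcome. Nor does it supply a patient count for level 3.

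It is also fair that item 5 speaks only of the MTD, so the RD conflict arises only because item 4 pairs the two. The percentages matter only if item 5 is applied literally. They also leave out level 3 ending at 1/6, which would add about 6 to 12 points at 10/20/40% (0.906 × 0.709 × 0.093 = 0.060, doubled if six are required), so they understate the full disagreement. The reference in section 6.1.1 to a section 7.1.2 that does not exist is clerical and adds no ambiguity of its own.

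**Conclusion.** The concern holds: the decision rule for the primary endpoint is wrong as written and must be fixed. At exactly 1/6, and at 0/3 on level 3, the documents do not give one answer. Under the assumed 10/20/40% rates, items 4 and 5 conflict over a declared level 1 or 2 in 36% or 39% of trials, depending on the unstated level-3 rule. These figures assume that item 4 is repeated when needed and that item 5 triggers no further step-down.

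Enrollment was planned to end in October 2018 and this version is dated April 2020; the actual status is not known from the documents. If enrollment has closed, the effect is on how the primary result is defined and reported, not on dose assignment.

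**What to change.** Reconcile items 2–5 of section 6.1.2 and the Summary to one MTD definition with one DLT count:

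- Use a separate term in items 2–3 if they mean that the MTD is exceeded.
- State in section 6.1.2 what follows 1/6.
- State how many DLT-evaluable patients are required at the level declared RD, including after 0/3 at level 3.
- Give the same total in the Summary, section 2.8.2 and section 12.8, consistent with Table 6.1.1a.
- Correct the section 7.1.2 reference in section 6.1.1.

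The choice of rule belongs to the sponsor; the requirement is that the passages agree. If escalation is complete, the clinical study report should state the rule that was applied.

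The cost is a wording amendment. It adds up to three patients at level 3 if six are required there, and possibly more at lower levels if the item 5 threshold is kept.
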